K-161-2.01US

A Phase 2, Prospective, Double-Masked, Randomized, Multi-Center, Vehicle-Controlled, Parallel-group, 4-week Administration Study Assessing the Safety, Efficacy, and Optimum Dosage of K-161 in non-Japanese and Japanese Adult Subjects with Moderate to Severe Dry Eye Disease Both in Environmental and Controlled Adverse Environmental (CAE[®]) Settings

NCT #: 04084483

Clinical Trial Protocol

Amendment 2

26 July 2019

Clinical Trial Protocol: K-161-2.01US

A Phase 2, Prospective, Double-Masked, Randomized, Multi-Center, Vehicle-Controlled, Parallel-group, 4-week Administration Study Assessing the Safety, Efficacy, and Optimum Dosage of K-161 in non-Japanese and Japanese Adult Subjects with Moderate to Severe Dry Eye Disease Both in Environmental and Controlled Adverse Environmental (CAE[®]) Settings

Protocol Title:

Protocol Number:

K-161-2.01US / [REDACTED]

Study Phase:

2

Investigational Product Name:

K-161

JND/IDE/PMA Number:

138738

Indication:

Dry eye disease

Investigators:

Multi-Center

Kowa Research Institute, Inc. (KRI)

Sponsor:

1. **What is the primary purpose of the study?** (Please select one)

[REDACTED]

[REDACTED]

Date _____

Original Protocol: 14 September 2018

Amendment 1: 13 June 2019

Amendment 2: 26 July 2019

Confidentiality Statement

This protocol contains confidential, proprietary information of [REDACTED] and/or Kowa Research Institute, Inc. Further dissemination, distribution or copying of this protocol or its contents is strictly prohibited.

SPONSOR PERSONNEL

[REDACTED]

[REDACTED]

[REDACTED]

MEDICAL MONITOR

[REDACTED]

SYNOPSIS

Protocol Title:	A Phase 2, Prospective, Double-Masked, Randomized, Multi-Center, Vehicle-Controlled, Parallel-group, 4-week Administration Study Assessing the Safety, Efficacy, and Optimum Dosage of K-161 in non-Japanese and Japanese Adult Subjects with Moderate to Severe Dry Eye Disease Both in Environmental and Controlled Adverse Environmental (CAE) Settings
Protocol Number:	K-161-2.01US / [REDACTED]
Investigational Product:	1. K-161 Ophthalmic Solution 2. Placebo Ophthalmic Solution (Vehicle)
Study Phase:	2
Objective(s):	The objective of the study is to assess the safety, efficacy, optimum dosage, and dosing regimen of K-161 compared to its vehicle from Day 1 (baseline) to Day 29 in non-Japanese and Japanese adult subjects with moderate to severe dry eye disease both in environmental and CAE settings.
Overall Study Design:	
Structure:	Prospective, double-masked, randomized, multi-center, vehicle-controlled, parallel-group study
Duration:	An individual subject's participation is estimated to be approximately 6 weeks (42 days) with a follow-up phone call.
Controls:	Placebo Ophthalmic Solution (Vehicle)
Dosage/Dose Regimen/ Instillation/Application/Use:	Subjects eligible to be randomized will receive one of the following treatments to be administered bilaterally for 28 days (from Visit 2 to Visit 5). 1) [REDACTED] K-161 Ophthalmic Solution; [REDACTED] [REDACTED] [REDACTED] 2) [REDACTED] K-161 Ophthalmic Solution; [REDACTED] [REDACTED] [REDACTED] 3) [REDACTED] K-161 Ophthalmic Solution; [REDACTED] [REDACTED] [REDACTED] [REDACTED] 4) Placebo Ophthalmic Solution (Vehicle); [REDACTED] [REDACTED] [REDACTED] During a 14-day study run-in period (for the purpose of subject selection) prior to randomization, all subjects will receive Placebo

[figure not shown]
	Ophthalmic Solution (Vehicle) [REDACTED] [REDACTED] [REDACTED]
Summary of Visit Schedule:	5 visits over the course of approximately 6 weeks with a follow-up phone call. 
• Visit 1 = Day -14 ± 2, CAE Screening• Visit 2 = Day 1, CAE Confirmation/ Baseline• Visit 3 = Day 8 ± 1• Visit 4 = Day 15 ± 2• Visit 5 = Day 29 ± 2• Follow-up Phone Call = Day 36 ± 2
Measures Taken to Reduce Bias:	This is a double-masked, randomized treatment assignment study.
Study Population Characteristics:	
Number of Subjects:	Approximately 600 subjects will be screened to enroll approximately 240 (60 per treatment arm*) subjects [REDACTED]
Condition/Disease:	Dry Eye Disease (DED)
Inclusion Criteria:	
Subjects who meet all of the following criteria will be eligible to participate in the study.	
Subjects must:	

1. Be at least 18 years of age at the time of informed consent visit
2. Have a reported history of dry eye disease in both eyes [REDACTED]
[REDACTED] and a history of eye drop use for dry eye symptoms [REDACTED]

Exclusion Criteria:

Subjects who meet any of the following criteria will not be eligible to participate in the study.

Subjects must not:

Evaluation Criteria:	
	
Primary Efficacy Endpoints:
 
The primary efficacy endpoint (sign) is:
 
• Change in inferior corneal staining score from Day 1 (baseline) to Day 29 by comparing [REDACTED] K-161 [REDACTED] to its vehicle [REDACTED] in CAE setting 
The primary efficacy endpoint (symptom) is:
 
• Change in Ora Calibra® ODS from Day 1 (baseline) to Day 29 by comparing [REDACTED] K-161 [REDACTED] to its vehicle [REDACTED] [REDACTED] in CAE setting
Efficacy Measures and Endpoints:	
Important Secondary Efficacy Endpoints:
 
The important secondary efficacy endpoints are:
 
• Change in Schirmer's Test value (unanesthetized) from Day 1 (baseline) to Day 29 by comparing [REDACTED] K-161 [REDACTED] [REDACTED] to its vehicle [REDACTED] in environmental setting• Change in TFBUT from Day 1 (baseline) to Day 29 by comparing [REDACTED] K-161 [REDACTED] to its vehicle [REDACTED] in CAE setting 
Secondary Efficacy Endpoints:
 
The secondary efficacy endpoints are comparisons of the following associated with taking the vehicle [REDACTED] and K-161 [REDACTED] (i.e., [REDACTED] K-161 [REDACTED] and [REDACTED] K-161 [REDACTED] for:
 
• Fluorescein staining by region: central, superior, inferior, temporal, nasal and corneal sum as assessed by the Ora Calibra® Corneal and Conjunctival Staining Scale• Lissamine green staining by region: central, superior, inferior, temporal, nasal, and conjunctival sum as assessed by the Ora Calibra® Corneal and Conjunctival Staining Scale• Conjunctival Redness as assessed by the Ora Calibra® Scale• TFBUT

	
• Tear Osmolarity• Schirmer's Test (unanesthetized)• Blink Rate• Ora Calibra® Ocular Discomfort Scale• Ora Calibra® Ocular Discomfort and 4-Symptom Questionnaire• Visual Analog Scale (VAS)
▪ Burning/ Stinging▪ Itching▪ Foreign Body Sensation▪ Blurred Vision▪ Eye Dryness▪ Photophobia▪ Pain• OSDI[©]
Safety Measures:	
■ [REDACTED]■ [REDACTED]■ [REDACTED]• Adverse event query■ [REDACTED]■ [REDACTED]■ [REDACTED]■ [REDACTED]

	
• Maximum dose tolerability by comparing the [REDACTED] K-161 [REDACTED] arm to the [REDACTED] and [REDACTED] K-161 [REDACTED] arms
Other:	[REDACTED]

Analysis Populations

- Intent-to-Treat Population – The intent-to-treat (ITT) population includes all randomized subjects. The primary analysis will be performed on the ITT population. Subjects in the ITT population will be analyzed as randomized.
- Per Protocol Population – The per protocol (PP) population includes subjects in the ITT population who do not have significant protocol deviations and who complete the study. Protocol deviations will be assessed prior to database lock and unmasking. Subjects in the PP population will be analyzed as treated.
- Safety Population – The safety population includes all subjects who have received at least one dose of the investigational product. The safety population will be analyzed for all safety assessments. Subjects in the Safety population will be analyzed as treated.

Sample Size

This study is expected to enroll 240 subjects in a 1:1:1:1 ratio across four treatment arms, or 60 subjects per treatment arm. In addition, randomization will be stratified such that [REDACTED] will be randomized in each treatment arm.

The standard deviation for change from baseline in post-CAE inferior corneal fluorescein staining ranges between 0.68 and 0.81 units. Assuming a common standard deviation of 0.77, a sample size of 60 subjects per group will have approximately 90% power to detect a difference of 0.46 units between the active treatment group and the vehicle group using a two-sample t-test at a two-sided significance level of 0.05. Again, it is assumed that adjusting for baseline and site will further reduce variability and provide >90% power.

Likewise, the standard deviation for change from baseline scores in the post-CAE ODS at Day 29 is assumed a common standard deviation of 0.82, a sample size of 60 subjects per group will have approximately 90% power to detect a difference of 0.49 units between the active treatment group and the vehicle group using a two-sample t-test at a two-sided significance level of 0.05. It is assumed that adjusting for baseline and site will further reduce variability and provide >90% power.

Multiplicity Consideration:

Common factors for multiplicity are multiple arms and multiple endpoints.

1) Multiple arms

The primary treatment comparison will be between the █ K-161 █ treatment arm and the vehicle █ treatment arm. Other treatment comparisons will be considered secondary or exploratory.

2) Multiple endpoints

The primary and important secondary endpoints will be tested hierarchically to maintain the study-wise Type I error rate of 0.05. First, change from baseline in inferior corneal fluorescein staining will be tested at an alpha level of 0.05. The test for change from baseline scores in the ODS will be conducted at an alpha level of 0.05 only if the previous test demonstrates significance. The test for change from baseline in Schirmer's test will be conducted at an alpha level of 0.05 only if the previous test demonstrates significance. The test for change from baseline in TFBUT will be conducted at an alpha level of 0.05 only if the previous test demonstrates significance. All other secondary and exploratory endpoints and treatment comparisons will be considered exploratory.

The hierarchical testing order will be as follows:

Primary comparisons:

1. Comparison of the change from baseline in post-CAE inferior corneal staining at Day 29 (█ K-161 █ vs vehicle)
2. Comparison of the change from baseline in post-CAE ocular discomfort at Day 29 (█ K-161 █ vs vehicle)

Important Secondary comparisons:

3. Comparison of the change from baseline in pre-CAE Schirmer's test value at Day 29 (█ K-161 █ vs vehicle)
4. Comparison of the change from baseline in post-CAE TFBUT at Day 29 (█ K-161 █ vs vehicle)

Thus, the study-wise Type I error rate will be maintained at 0.05 by considering only one dose of K-161 as the primary treatment comparison and using a hierarchical testing procedure.

Primary Efficacy Analyses:

The primary comparisons of change from baseline in post-CAE inferior corneal staining and ocular discomfort between the █ K-161 █ group and the vehicle group at Day 29, will be performed using analysis of covariance (ANCOVA) models. The respective baseline post-CAE score will be included as a covariate in each model and site will be included as a fixed effect. Treatment by baseline and treatment by site interactions will be explored in separate models and, if significant, analyses will be performed by baseline stratification and/or site, respectively, to further examine significant interactions. The primary analyses will use the ITT population.

For the primary endpoints multiple imputation with a control-based pattern mixture model will be used.

Secondary Efficacy Analyses

[figure not shown]
Secondary and exploratory efficacy endpoints will be analyzed similarly to the primary analyses on the ITT population. Continuous and ordinal variables collected at each visit will be summarized descriptively (n, mean, standard deviation, median, minimum and maximum), and analyzed with ANCOVA models each K-161 █ group to the vehicle group. All visit-based data will be analyzed by visit and for each timepoint, if applicable, as well as the change from baseline.

Data collected pre- and post-CAE will also be analyzed for the change from pre- to post-CAE within each visit. Data collected during the CAE will also be analyzed using repeated measures models including all of the time points from a CAE exposure.

For the two important secondary endpoints, other secondary, and exploratory endpoints, multiple imputation with a control-based pattern mixture model will be used.

Safety Variables

Adverse events (AEs) will be coded using the MedDRA dictionary. Frequencies and percentages of subjects with treatment-emergent adverse events (TEAEs), serious TEAEs, and TEAEs causing premature discontinuation will be provided by treatment group. An AE is treatment emergent if it occurs or worsens after the first dose of study treatment. Furthermore, frequencies will be given of subjects with TEAEs by system organ class; by system organ class and preferred term; by system organ class, preferred term and maximal severity; by system organ class and preferred term for treatment-related TEAEs; and by system organ class, preferred term, and study day of onset. Separate summaries will be performed for ocular and non-ocular AEs.

Other analyses may be conducted and the details will be included in a separate statistical analysis plan.

TABLE OF CONTENTS

SYNOPSIS.....	3
TABLE OF CONTENTS.....	14
LIST OF ABBREVIATIONS.....	18
1 INTRODUCTION	20
1.1 Drug Profile from Non-clinical Studies	20
2 STUDY OBJECTIVES.....	21
3 CLINICAL HYPOTHESES	21
4 OVERALL STUDY DESIGN	21
5 STUDY POPULATION	22
5.1 Number of Subjects (approximate)	22
5.2 Study Population Characteristics.....	22
5.3 Inclusion Criteria.....	22
5.4 Exclusion Criteria.....	24
5.5 Withdrawal Criteria (if applicable)	25
6 STUDY PARAMETERS.....	26
6.1 Efficacy Endpoints	26
6.1.1 Primary Efficacy Endpoints.....	26
6.1.2 Important Secondary Efficacy Endpoints	26
6.1.3 Secondary Efficacy Endpoints.....	26
6.1.4 Exploratory Efficacy Endpoints.....	27
6.2 Safety Measures	27
6.3 Other Measures.....	27

MedDRA	Medical Dictionary for Regulatory Activities
NCS	Not clinically significant
ODS	Ocular Discomfort Score
OSDI	Ocular Surface Disease Index
OTC	Over the counter
PP	Per protocol
SAE	Serious adverse event
SOP	Standard operating procedure
TFBUT	Tear film break-up time
WHO	World Health Organization

1 INTRODUCTION

Dry eye disease (DED) is a multifactorial, progressive disorder of the ocular surface resulting from insufficient tear coverage of the surface of the eye in combination with ocular surface inflammation. Patients with DED often experience severe pain, visual impairment, tear film hyperosmolarity and instability, inflammation, and corneal wounding. While the prevalence of DED is difficult to report due to varying definitions and diagnostic criteria, the global prevalence of DED is estimated to be between 5% and 50%, and increases with age (Bron et al. 2017). In the United States, it is estimated that as many as 3.2 million women and 1.7 million men over the age of 50 have DED, with a projected 40% increase in number of patients affected by 2030 (Schaumberg et al. 2002, Schaumberg et al. 2003, Schaumberg et al. 2009).

Current treatment and management of DED consists primarily of tear supplementation with lubricants (artificial tears). While artificial tears improve symptoms associated with DED, they have no effect on resolving the underlying conditions that lead to inflammation of the ocular surface. Three currently available options for treating inflammation at the ocular surface are Restasis® (cyclosporine ophthalmic emulsion) CEQUA™ (cyclosporine ophthalmic solution), and Xiidra® (lifitegrast ophthalmic solution). It has been shown that only 15% of patients respond to Restasis® after 6 months of treatment, as measured by Schirmer's test, and many more report ocular side-effects such as burning and stinging (Mah et al. 2012). Xiidra® has also been shown to be associated with ocular adverse events (AEs); in a clinical study of Xiidra® for subjects with DED, subjects reported increased ocular irritation upon instillation with Xiidra® compared to placebo (7.8% compared to 1.4% in the placebo group) (Tauber et al. 2015). Similarly, common adverse reactions reported after use of CEQUA include instillation site pain and conjunctival hyperemia (CEQUA 2018). Thus, there remains a medical need for more efficacious treatment options with a more favorable safety and comfort profile for patients with DED.

1.1 Drug Profile from Non-clinical Studies

[REDACTED] a tyrosine kinase involved in cytokine signaling and activation of lymphocytes. [REDACTED] have been shown to have potent anti-inflammatory activity both *in vitro* and *in vivo* ([REDACTED] [REDACTED]). Tofacitinib, a [REDACTED] [REDACTED], was shown to suppress ocular surface inflammation and corneal injury in a mouse model of dry eye disease ([REDACTED]). Because inflammation is a key component of DED, targeting the inflammatory pathway via [REDACTED] to reduce cytokine production and/or immune cell infiltration at the ocular surface may reduce the signs and symptoms of DED.

[REDACTED]
[REDACTED]
[REDACTED]
[REDACTED]
[REDACTED]
[REDACTED]
[REDACTED]

This will be the first clinical study of K-161 Ophthalmic Solution.

2 STUDY OBJECTIVES

Prior to any changes in a subject's medical treatment and/or study visit procedures, the study will be discussed with each subject and subjects wishing to participate must give written informed consent (and/or assent) and sign a Health Insurance Portability and Accountability Act (HIPAA) form.

The objectives of the study are to assess the safety, efficacy, optimum dosage, and dosing regimen of K-161 compared to its vehicle from Day 1 (baseline) to Day 29 in non-Japanese and Japanese adult subjects with moderate to severe dry eye disease both in environmental and Controlled Adverse Environment (CAE) settings.

3 CLINICAL HYPOTHESES

The clinical hypotheses for this study is that [REDACTED] K-161 Ophthalmic Solution [REDACTED] [REDACTED] is superior to its vehicle ([REDACTED] for the primary endpoints of signs and symptoms of dry eye, as follows:

- Sign: Post-CAE inferior corneal fluorescein staining score on the Ora Calibra® scale, measured by mean change from baseline (Visit 2) to Visit 5
- Symptom: Post-CAE ocular discomfort scale on the Ora Calibra® scale, measured by mean change from baseline (Visit 2) to Visit 5

4 OVERALL STUDY DESIGN

This is a Phase 2, multicenter, randomized, double-masked, vehicle-controlled, parallel-group design with block enrollment. Subjects will be randomized to one of the following treatment groups at Visit 2:

- [REDACTED] K-161; [REDACTED] (N=~60)
- [REDACTED] K-161; [REDACTED] (N=~60)
- [REDACTED] K-161; [REDACTED] (N=~60)
- Placebo Ophthalmic Solution (Vehicle); [REDACTED] (N=~60)

Approximately 240 subjects will be randomly assigned to one of the four treatment groups (1:1:1:1). [REDACTED]

[REDACTED] Subjects, Sponsor, Contract research organization (CRO), and site personnel will be masked to treatment assignment. To ensure masking, a dedicated unmasked staff member/technician will be delegated to dispense and observe instillation of randomized study drug and collect randomized study drug from a subject for drug accountability. This person cannot perform any other study-related procedures. Additionally, the informed consent form (ICF) will not indicate any relationship between dosing regimen and treatment. Subjects will be instructed not to discuss their assigned dosing regimen or perceived treatment effects with other study participants.

During the screening period, two 90-minute exposures to the CAE will be conducted to ascertain eligibility to enter the study. Subjects who qualify after the initial screening visit will enter the run-in phase, where they will self-administer vehicle [REDACTED] for approximately 14 days. Those who qualify at Visit 2 (Day 1) will be randomized to receive study drug in a double-masked fashion for 28 days. Randomization will be stratified on Visit 2 Post-CAE inferior fluorescein staining and

Post-CAE ocular discomfort on the Ora Calibra® scale. Subjects will self-administer drops either [redacted] or [redacted]

At Visit 4 (Day 15) and Visit 5 (Day 29), CAE exposure will occur, with pre-CAE, during CAE (symptoms only) and post-CAE assessments of ocular signs and symptoms. At Visit 3, no CAE exposure will occur but signs and symptoms will be assessed. Study drug will be discontinued at Visit 5. Subjects will exit from the study at this visit. The follow-up phone call will occur about 7 days after the final day of randomized study drug treatment.

The timing of subject visits and examinations will be consistent throughout the study.

5 STUDY POPULATION

5.1 Number of Subjects (approximate)

It is estimated that approximately 600 subjects will be screened to enroll approximately 240 randomized subjects (60 in each group). █

Subjects will be randomized in a 1:1:1:1 ratio of

- [REDACTED] K-161; [REDACTED]
- [REDACTED] K-161; [REDACTED]
- [REDACTED] K-161; [REDACTED]
- Placebo Ophthalmic Solution (Vehicle);

5.2 Study Population Characteristics

All subjects must be at least 18 years of age, of either gender, and of any race, and must meet all inclusion criteria and none of the exclusion criteria.

5.3 Inclusion Criteria

Each subject must:

1. Be at least 18 years of age at the time of informed consent visit
2. Have a reported history of dry eye disease in both eyes [REDACTED]
[REDACTED] and have a history of eye drop use for dry eye symptoms

A series of horizontal black bars of varying lengths, likely representing data points or categories in a list. The bars are arranged vertically and have small black squares at their left ends.

5.4 Exclusion Criteria

Each subject must not:

5.5 Withdrawal Criteria (if applicable)

If at any time during the study the investigator determines that a subject's safety has been compromised, the subject may be withdrawn from the study.

Subjects may withdraw consent from the study at any time.

Sponsor and/or investigator may discontinue any subject for non-compliance or any valid medical reason (see Section 8.6.2).

The subject has the right to withdraw from the study at any time. Nevertheless, in this study, every attempt will be made to prevent missing data and to obtain complete follow up of all subjects during the study period. Investigators will be trained to minimize full withdrawals from the study period wherever possible. Subjects who discontinue study drug during the study period are not required to withdraw from the study. These subjects will be encouraged to remain in the study and asked to conduct the remaining study visits as outlined in the protocol through Visit 5. If a subject fails to actively maintain contact with the Investigator, reasonable efforts (telephone calls to family members or friends, e-mail contacts, etc.) will be made in order to encourage the subject to complete the study visits.

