8.5 Compliance with Protocol

Subjects will be given written instructions; instructed on proper instillation; and instructed on proper storage of the IP at the end of Visits 1, 2, 3, and 4. The subject used/unused [REDACTED] will be collected at each visit from Visit 2 up to and including Visit 5 to assess dosing compliance. Dosing compliance will be based on [REDACTED]. If the subject is less than 80% or more than 125% compliant with dosing based on [REDACTED], then the subject will be deemed non-compliant and a dosing deviation should be recorded in the source document. The investigator will use these guidelines to determine subject study compliance and deviation compliance.

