8.6.2 Discontinued Subjects

Subjects may be discontinued prior to their completion of the study due to:

- subject request/withdrawal
- AEs
- protocol violations
- administrative reasons (e.g., inability to continue, lost to follow up)
- sponsor termination of study
- other

Note: In addition, any subject may be discontinued for any sound medical reason.

Notification of a subject discontinuation and the reason for discontinuation will be reported to [REDACTED] and/or the Sponsor and clearly documented on the electronic case report form (eCRF).

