9.4 Procedures for Unmasking (if applicable)

All subjects, investigators, and study personnel involved with the conduct of the study will be masked with regard to treatment assignments. When medically necessary, the investigator may need to determine what treatment group has been assigned to a subject. When possible (i.e., in non-emergent situations), █ and/or the Sponsor will be notified before unmasking the investigator. █ and/or the Sponsor must be informed immediately about any unmasking event.

If the investigator identifies a medical need that requires unmasking the treatment assignment of a subject, █ and/or the medical monitor will be contacted prior to unmasking the identity of the IP, if possible. █ will ask the staff to complete and send them the Unmasking Request Form. █ will notify the Sponsor and jointly determine if the unmasking request should be granted. In addition, they may consult the medical monitor as needed. The result of the request will be documented on the Unmasking Request Form. If approval is granted to unmask a subject, written permission will be provided on the Unmasking Request Form. The investigator will unmask the subject using the interactive web response system (IWRS), complete the Unmasking Memo form, include it in the subject's study file and make a copy for the trial master file (TMF). For each unmasked request, the reason, date, signature, and name of the person unmasking the subject must be noted in the subject's study file.

Unmasked subjects will be discontinued from the study and followed for safety monitoring, until resolution of the AE or study completion, whichever occurs last.

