Subject disposition will be presented in terms of the numbers and percentages of subjects who were randomized to blinded study medication with subcategories of dosed with the blinded study medication, did not dose with blinded study medication; who were included in the following analysis populations: ITT, PP, safety, [REDACTED] and who completed the study and discontinued from the study. Subjects who are not discontinued from the study will be considered study completers. Disposition will be summarized by treatment group and for all subjects. Percentages will be calculated using randomized subjects as the denominator unless otherwise specified.

The total number of enrolled subjects and screen failed subjects will be presented.

The reasons for premature study discontinuation will be summarized by treatment group for all discontinued subjects. Percentages will be calculated using discontinued subjects as the denominator. The reasons for study discontinuation that will be summarized include: AE, Subject Request/Withdrawal, Protocol Violation(s), Administrative Reasons, Sponsor Termination of Study, and Other. A subject listing will be provided that includes the date of and reason for premature study discontinuation.

The number and percentage of subjects with any deviation, major deviation, and minor deviation will be summarized by treatment group for all randomized subjects. The protocol deviations that will be summarized include the following categories: Informed Consent, Inclusion/Exclusion and Randomization, Test Article/Study Drug Instillation and Assignment at Site, Improper Protocol Procedures at Site, Site's

Failure to Report Serious Adverse Event (SAE)/AE, Visit Out of Window, Subject's Non-compliance with Test Article/Study Drug, Subject's Use of Prohibited Concomitant Medication, Subject's Failure to Follow Instructions, and Other. A subject listing will be provided that includes the date of the deviation, the deviation code, the deviation description, and the classification of whether the deviation was judged to be major or minor in a masked review.

In addition, subject listings will be provided that include informed consent date, inclusion and exclusion criteria violations, exclusions from the PP population, and screen failures. Details of the study randomization, including randomization date and time, and randomized treatment, will also be included within a subject listing.

10. Demographic and Pretreatment Variables

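### Protocol 5.5 aims at complete follow-up, yet 5.5, 8.6.2 and 9.4 let or make subjects leave the study for reasons that do not prevent a Day 29 assessment

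*Protocol*

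**What the plan says.** Protocol 5.5 states that "every attempt will be made to prevent missing data and to obtain complete follow up of all subjects during the study period". It separates treatment from follow-up: "Subjects who discontinue study drug during the study period are not required to withdraw from the study". It also says that investigators will be trained to keep full withdrawals to a minimum, and that subjects off drug will be asked to attend through Visit 5.

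Three routes out of the study sit beside this:

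- **Non-compliance (permitted).** Protocol 5.5: "Sponsor and/or investigator may discontinue any subject for non-compliance or any valid medical reason", with a reference to 8.6.2.
- **Protocol violations (permitted).** Protocol 8.6.2 opens with "Subjects may be discontinued prior to their completion of the study due to" and lists "protocol violations" among the reasons. SAP 9 tabulates the same category as a reason for study discontinuation.
- **Unmasking (mandatory).** Protocol 9.4: "Unmasked subjects will be discontinued from the study and followed for safety monitoring". SAP 4.2 repeats it.

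Protocol 8.5 defines non-compliance ("If the subject is less than 80% or more than 125% compliant with dosing") and asks for a dosing deviation to be recorded. It does not itself call for removal.

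The ITT population is all randomized subjects (Protocol 10.1, SAP 7.1). SAP 13.1.1 imputes missing Day 29 staining with a control-based pattern mixture model, and 13.1.2 does the same for ODS.

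**The concern.** Non-compliance, a protocol violation and an unmasking event are facts about how treatment or conduct went. A subject who still consents can, in general, attend the remaining visits after any of them. Section 5.5 recognises this for subjects who stop study drug, but the distinction is not carried into the three routes above. A subject who could have been observed at Day 29 then has a missing primary outcome.

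Under the SAP's imputation code the missing score is drawn from a regression fitted to vehicle subjects. For a removed K-161 subject, an outcome that could have been measured is replaced by a vehicle-like one. What is at stake is precision and dilution of the estimated effect on both primary endpoints. Later analysis cannot recover an outcome that was never collected.

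**Working it through.** **1. Are the removals at study level?** Section 8.6.2 concerns leaving before completion of the study, and 9.4 says discontinued from the study. The sentence in 5.5 does not say so itself, but it stands under withdrawal criteria and refers to 8.6.2. All three routes are therefore study-level.

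**2. What happens to the Day 29 value?** Visit 3 has no CAE exposure (Protocol 4), so after baseline the post-CAE primary scores are scheduled only at Visits 4 and 5. The imputation model in SAP 13.1.1 uses baseline, Visit 4 and Visit 5, with the vehicle arm as the modelling group.

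- A K-161 subject removed before Day 15 without a usable post-CAE score is imputed from baseline and the vehicle regression alone.
- One removed after Day 15 keeps an observed Visit 4 score, which carries part of any effect forward.

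Protocol 8.3.7 asks for Visit 5 safety and further (redacted) evaluations on the day of discontinuation or at the investigator's discretion. That is not a Day 29 value, and the visible SAP text has no rule placing it at Day 29.

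Protocol 10.4.5 describes MCMC imputation by arm instead, but 10.4.3 and the SAP specify the control-based model, and SAP 1 says the SAP supersedes. The dilution below rests on the SAP method.

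**3. The plan's own power.** Inputs from Protocol 10.3 and SAP 5: n = 60 per arm, two-sided alpha 0.05; staining difference 0.46, SD 0.77; ODS difference 0.49, SD 0.82. No allowance for missing data is stated. For a two-sample t-test:

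- noncentrality = difference / (SD × √(2/60)), with 118 degrees of freedom and critical value 1.980
- staining: 0.46 / (0.77 × 0.18257) = 3.272, power 90.1%
- ODS: 0.49 / (0.82 × 0.18257) = 3.273, power 90.1%

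The stated figure of about 90% reproduces for both.

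**4. Upper bound on the loss.** Let m be the share of the active arm removed by these routes. The documents give no rate, so m is an assumption. If removed subjects are imputed with no active effect, the expected difference is 0.46 × (1 − m). As a rough approximation n stays at 60 and the SD at 0.77.

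| m (subjects of 60) | Difference | Power |
|---|---|---|
| 0 | 0.460 | 90.1% |
| 2.5% (1.5) | 0.449 | 88.6% |
| 5% (3) | 0.437 | 86.9% |
| 10% (6) | 0.414 | 83.2% |

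The ODS figures agree within 0.1 point.

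**5. A fairer comparator.** Step 4 compares removal with a world in which those subjects would have shown the full 0.46. Non-compliers observed under ITT might show less. If they kept half the effect (an assumption), the difference without removal is 0.46 × (1 − m/2). The loss due to removal, from unrounded powers, is then:

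| m | Power if observed | Power if removed | Loss, half effect | Loss, full effect |
|---|---|---|---|---|
| 2.5% | 89.3% | 88.6% | 0.8 points | 1.5 points |
| 5% | 88.6% | 86.9% | 1.6 points | 3.1 points |
| 10% | 86.9% | 83.2% | 3.8 points | 6.9 points |

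**The case against.** The other side has real points.

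- **Two routes are only permissive.** Sections 5.5 and 8.6.2 say that subjects may be discontinued, and 5.5 tells investigators to minimise withdrawals. For those routes this is a tension, not a flat contradiction. It stands, but the permission does not need to be there.
- **Much of the remedy already exists.** Protocol 8.5 asks only for a recorded deviation, and the PP population handles significant ones. That stands, and it also shows that ending follow-up serves no analytic purpose.
- **Unmasking has a rationale.** It is reserved for medical need, and the ODS is rated by the subject, so scores after unmasking are open to expectation bias that a masked assessor cannot cure. This stands and shapes the fix.
- **Sensitivity analyses are planned.** Observed-case, LOCF, MAR imputation and tipping-point analyses probe the missing data but do not replace the uncollected outcome.

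Three stronger readings are tempting and not supported.

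- **Unequal dosing burden in the primary comparison.** SAP 12.1 has four-dose and two-dose formulas, so a reader might infer unequal removal between the primary K-161 arm and vehicle. The arm labels are redacted, and the wording of SAP 12.1 with the heading of SAP 14.1.4 suggests a single four-times-daily arm, with the primary comparison probably at equal frequency.
- **Removal steered by knowledge of treatment.** Sponsor, CRO and site staff other than the dispensing technician are masked, and SAP 9 has deviations classified in masked review.
- **Eligibility failures named as a ground for removal.** Section 8.6.2 says only protocol violations. SAP 9 lists "Inclusion/Exclusion and Randomization" as a deviation category, so eligibility errors are a likely subset and no more.

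**Conclusion.** The point holds as a gap between the follow-up aim of 5.5 and the removal rules in 5.5, 8.6.2 and 9.4. It is mandatory for unmasking and discretionary for the other two routes. The consequence is avoidable missing Day 29 data and dilution toward no effect; a reader might infer a raised false-positive risk, but the mechanism examined here does not show one.

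The size is uncertain. The fall from 90.1% to between 88.6% and 83.2% is an upper bound that rests on an assumed removal rate of 2.5% to 10%, on imputed values carrying no active effect, and on a full-effect comparator. Observed Visit 4 scores, or a weaker effect in the removed subjects, make it smaller. The inconsistency does not depend on these figures. It should be corrected because the change is cheap and carries out what 5.5 says it intends.

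**What to change.** Reconcile Protocol 5.5, 8.6.2 and 9.4 and SAP 4.2, keeping the end of study drug distinct from the end of study follow-up.

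- **Non-compliance and protocol violations.** Remove them as reasons to end follow-up. These subjects keep the scheduled Visit 4 and Visit 5 assessments unless consent is withdrawn or the investigator judges the visit unsafe. They stay in ITT, and the deviation is recorded and handled through the PP population.
- **Unmasked subjects.** Reconcile 9.4 with the aim of 5.5. If Day 29 data are collected, flag them and add a sensitivity analysis excluding them, mainly because of the self-rated ODS.
- **Study drug.** Decisions about it are left as they are.

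The cost is protocol and SAP wording, a matching change to the disposition categories in SAP 9, site training and one extra sensitivity table. The visits are already scheduled. The small downside is that any data collected after unmasking are less trustworthy, which the flag and the sensitivity analysis make visible.
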